4.1 Selection of participants

Recruitment

Mothers and their newborns will be recruited by MRC Infant Immunology group's field site at Faji Kunda health centre, located in a peri-urban area in The Gambia. Field workers and nurses known to the local community will do sensitization of mothers to the study. Government staff working in the antenatal clinic and on the labour ward at the health centre may provide additional information. When possible, field workers/nurses will talk to potential participants and their families in advance of the delivery to sensitize them to the study and to provide them with a copy of the informed consent document. If a pregnant woman is interested in the study, a sticker will be placed in her yellow antenatal record card. She will also be given a card with contact numbers for the study staff. The study team will be contacted when women present in labour either by the women themselves, or the midwives on duty. Mothers presenting to the health centre in labour

may additionally be sensitized to the study if this has not occurred in advance and when adequate time is available.

Oral consent will be gained from the mothers at the time of delivery in order to collect rectovaginal swabs before delivery and cord blood (which has to be processed within 6 hours of collection). The midwives will collect cord blood samples on duty or by a member of the study team. Written informed consent will then be obtained by a fieldworker/nurse shortly after birth, when they have recovered sufficiently and will include consent to collect a nasopharyngeal and rectal swab from the newborn and to collect breast milk. Final enrolment will occur after informed consent has been obtained and only if the neonate meets the inclusion criteria and does not meet any of the exclusion criteria (see below).

They will be asked to provide further informed consent to a nasopharyngeal and rectal swab of the newborn and collection of breast milk coinciding with the first postnatal check at approximately 6 days post-partum. A Final breast milk sample, infant venipuncture sample and nasopharyngeal and rectal swab will be taken at 2 months at the infant's first immunisation clinic visit.

4.2 Eligibility of participants

Newborns must meet all of the inclusion criteria and none of the exclusion criteria to be eligible to participate in the study.

4.2.1 Inclusion criteria

Maternal:

- 1. Written informed consent obtained from the infant's mother
- 2. Maternal age over 18 years
- 3. >37/40 gestation
- 4. Born to known HIV negative mothers (tested and documented on the yellow antenatal card in the current pregnancy

- 4. Ability to comply with the study procedures as judged by a member of the research team
- 5. Remaining in the Faji Kunda area for at least the first 12 weeks following delivery
- 6. Planning to breastfeed

Infant:

- 1. Singleton
- 2. Birth weight >=2.5kg
- 3. Healthy infants without congenital birth defects requiring prolonged hospital stay (>48 hours)

4.2.2 Exclusion criteria

- 1. Significant congenital abnormalities
- 2. Symptoms or signs of significant illness or infection
- 3. Planning to move outside the study area (preventing follow-up visits) during the 3 months of study participation
- 4. Enrollment in other studies requiring blood/breast milk sampling or swabs
- 5. Any other condition or situation meaning that participation would not be in the best interests of the infants
- 6. Any reason that would prevent the study endpoints being assessed in the infant effectively as judged by the investigator
- 7. Multiple Pregnancies
- 8. Complications of delivery (preeclampsia, antepartum hemorrhage, caesarian section)
- 9. Premature infants (born prior to 37 weeks gestation)
- 10. Bottle-fed infants
- 11. Known HIV infection
- 12. Birth weight <2.5kg.

4.3 Withdrawal of participants

A study participant will be discontinued from participation in the study if:

- Any medical condition or situation occurs such that continued participation in the study would not be in the best interest of the participant.
- Development of any exclusion criteria.

For further details on participant's premature termination see corresponding section below.

Participants are free to withdraw from the study at any time without giving a reason.

5 Study procedures and evaluations

For an overview see annex "Schedule of Events".

5.1 Study schedule

All infants will be followed-up at 3 time-points between births to age 3 months and will receive their EPI schedule normally as shown in Table 1.

5.1.1 Screening

[figure not shown]
Figure 4 - Sensitisation

5.1.2 Enrollment (Baseline)

[figure not shown]
Figure 5 - Visit 1

Consent and Samples Time Point 1

[figure not shown]
5.1.3 Follow-up - Visit 2

Figure 6 - Visit 2

5.1.4 Final study visit

Figure 7 - Visit 3

5.2 Study evaluations

A case report form will be completed at each time point. At the time of screening for study eligibility, the following information will be recorded on the appropriate case report form (CRF):

- Study mother demographic information
- Study mother medical information to include: Gestational age calculated by last menstrual period or midwife palpation or ultrasonography if available, gravida, parity, living children, HIV status, time of rupture of membranes prior to delivery, mode of delivery, antenatal risk factors for infection (Premature rupture of membranes/chorioamnionitis/maternal fever), information on maternal vaccination status, information of any infections leading up to delivery requiring antibiotics, current medication.
- Study infant demographic information

• Study infant medical information to include: gestational age, birth weight, perinatal complications (birth asphyxia/meconium staining/fever >38.5 degrees, hypothermia, poor feeding, floppiness, hypoglycaemia.

At each subsequent time point the following information will be recorded on the appropriate case report form (CRF):

- Feeding type
- Any overnight hospital admissions.
- Any episodes of malaria, septicaemia, pneumonia, meningitis, worms, otitis media, tonsillitis, upper respiratory tract infection (URTI)
- Any courses of intravenous or oral antibiotic therapy.
- Any current medications

5.2.1 Clinical evaluations

At recruitment a limited newborn examination will be performed by the study clinician or nurse as detailed in the screening record.

At each time-point infant anthropometry will be recorded including:

- Weight (grams)
- Head circumference/Occipitofrontal circumference (OFC) (cm)
- Length (cm)

At each time-point infant vital signs will be recorded including:

- Respiratory rate (breaths per minute)
- Oxygen saturations (%)
- Heart rate (beats per minute)
- Temperature (°C)

In addition to the study time-points the infants will be given their routine EPI vaccines by the study staff. The vaccine details will be recorded on their infant welfare card as well as in the study paperwork.

5.2.2 Laboratory evaluations

Swab culture

Rectovaginal swabs will be taken from all mothers at presentation in labour and sent same day to the MRC laboratory. Nasopharyngeal and rectal swabs will be taken from all infants and sent same day to the MRC laboratory. Maternal and infant swabs will be pre-cultured overnight in Todd Hewitt Broth and cultured by plating on selective blood agar plates for 48 hours. If there is any bacterial growth this will be identified as GBS by latex agglutination test and serotyping by RT-PCR.

Cord blood and at 2 to 3-months of age

Additional experiments will be done from the cord blood samples and from the infants at 3-months of age in order to complete the antibody aspect of this study. The blood samples will need to be transported to MRC laboratories in EDTA tubes within 6 hours of collection, spun down and frozen at -70 degrees. The samples will be batched and sent to Porton Down, UK for serotype-specific antibody analysis and complement deposition studies.

Breast milk

Additional experiments will be done from breast milk samples collected at birth, day 6 and day 60. Women will be asked to hand express 1-2mL of colostrum at the first visit and 4-5mL of breast milk on day 6 and day 60. Breast milk should be expressed from each breast and collected in two sterile universal containers. The samples need to go immediately into cold storage and transferred same day to the laboratory. The samples then need to be aliquoted into 100uL samples and frozen at -70 degrees. Batches of breast milk will then be sent to Porton Down for antibody analysis and complement deposition studies.

Sample handling Cord blood and 3 months

Spin sample, take off serum into two aliquots and PLACE SAMPLE STRAIGHT IN -70°C & RECORD LOCATION IN WORKSHEETS

Table 2 - Laboratory experiments

Experiment	Time course	Volume required	Method	Sample storage
1. Microbiological swab culture	48 hours (12-56 hours)	1 combined rectovaginal swab (mother) 1 nasopharyngeal swab, 1 rectal swab (infant)	See SOP	Store at 4 degrees until culture. Culture at 37 degrees
2. Antibody surface labeling studies	4 hrs (3.5- 4.5 hrs)	>2mL	See SOP	Serum in YELLOW tubes, spin down and aliquot into 2 aliquots and store at -70°C

3. Complement deposition studies	4 hrs (3.5- 4.5 hrs)	>2mL	See SOP	Serum in YELLOW tubes, spin
· ·	4.5 hrs)			
studies				down and
				aliquot into 2
				aliquots and
				store at -70°C

NB/ For full details of the full laboratory procedures please see the corresponding SOPs

6 Safety considerations

Morbidity will be closely monitored as a safety net for participants, and free access to basic health care will be provided to the mothers and their child. This includes basic medical treatment for non-severe infections (urinary, respiratory, malaria, skin infections *etc.*) provided at Faji Kunda clinic during opening hours (open Monday to Thursday 8am until 4pm, and Friday 8am to 12pm). If the infection is severe then the mother/child will need to be referred either to a government hospital or to the MRC site in Fajara for further assessment and/or hospital admission. In most cases, if the family incurs costs at referring facilities or out of hours centres, these costs will be reimbursed by the study team. The free health care will be provided to our participants until the child is 3 months of age, (including participants subsequently excluded) as well as 24/7 access to study staff via mobile phones.

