2.1 Study endpoints

1. Serotype-specific GBS colonisation in mothers and infants

Prevalence of serotype-specific GBS carriage in mothers and their infants and changes in infant carriage over time will be determined by culturing rectovaginal swabs and infant nasopharyngeal and rectal swabs in selective microbiological media for GBS.

2. Serotype-specific GBS antibody concentration

Serotype-specific GBS antibody-concentration (Ia, Ib, II, III, V) in blood and breast milk will be determined at each of the three time points using flow cytometry.

3. GBS-antibody function

Serotype-specific GBS antibody function (Ia, Ib, II, III, V) will be determined in blood and breast milk using complement C3b/C5 deposition and flow cytometric methods.

3 Study design

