3.1 Type of study and design

Study design

Study Design (See Figure 3 for study design).

This is a prospective cohort study, based at Faji Kunda Health Centre of pregnant women recruited at 37 weeks gestation from the antenatal clinic at Faji Kunda and their infants from birth to 3 months of life.

Interventions

- a. Samples in labour: combined rectovaginal swabs will be taken from mothers in labour and nasopharyngeal and rectal swabs their infants at birth. 1mL of colostrum taken within 72 hours of birth, 4-5 mL of cord blood.
- b. Samples at day 6: nasopharyngeal and rectal swabs from infants, 1-2 mL breast milk
- c. Samples at day 56-90: nasopharyngeal and rectal swabs from infants, 4-5 mL breast milk, 2-3mL infant serum

Data Collection

A case report form (CRF) will capture information on:

Epidemiological data:

a) maternal: Site of delivery, mode of delivery, antenatal risk factors for infection (Premature rupture of membranes/chorioamnionitis/maternal fever/raised white cell count), number of live births, information on maternal vaccination status, information of any infections leading up to delivery requiring antibiotics, time in hours of rupture of membranes prior to delivery.

b) infant: gestational age, birth weight, stillbirths/neonatal deaths/perinatal complications

(birth asphyxia/meconium staining/signs of severe infection in the first three months of life (fever >38.5 degrees, raised white cell count, meningism). Gestational age calculated by last menstrual period or midwife palpation or ultrasonography if available.

Sample Collection

- 1) Maternal/infant carriage:
 - a) Maternal swabs: Combined-vaginal-rectal swabs in labor from all mothers who have been consented in the antenatal clinic.
 - b) Infant swabs: nasopharyngeal and rectal swabs in the first 24 hours after birth of all infants whose mothers have been enrolled into the study, second infant swabs on day 6 and final infant swabs collected at day 48

[figure not shown]
2) Antibody Carriage Serum:

[figure not shown]
a) Maternal serum: Cord blood or maternal serum sample at delivery to determine antibody levels.

b) Infant serum: at two months using venipuncture.

3) Antibody Carriage Breast milk:

Breast milk will be collected at day 0, 6 days and 2-3 months post-partum. The women will be given non-sterile surgical gloves and asked to manually express several drops of milk, which were discarded before collecting the specimen directly into the test tube.

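### Section 5.2.2 sends the same cord and infant blood in EDTA tubes in its text but asks for serum in its handling note and Table 2, which puts the blood part of the complement-deposition endpoint at risk

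*Protocol*

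**What the plan says.** Section 5.2.2 of the Protocol gives three sets of instructions for the cord sample and the infant sample at 2-3 months.

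- The running text: "The blood samples will need to be transported to MRC laboratories in EDTA tubes within 6 hours of collection". It then has the samples spun and frozen, and names their use: "The samples will be batched and sent to Porton Down, UK for serotype-specific antibody analysis and complement deposition studies".
- The handling note for cord blood and 3 months: "Spin sample, take off serum into two aliquots and PLACE SAMPLE STRAIGHT IN -70°C". It names no tube.
- Table 2, antibody labelling row: "Serum in YELLOW tubes, spin down and aliquot into 2 aliquots and store at -70°C". The complement-deposition row begins the same way: "Serum in YELLOW tubes, spin". In both rows the entry stands in the storage column.

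Section 3.1 lists the day 56-90 infant sample as "2-3mL infant serum". Section 2.1 defines endpoint 3 as serotype-specific antibody function, which "will be determined in blood and breast milk using complement C3b/C5 deposition and flow cytometric methods". For assay detail the protocol refers to SOPs that are not among the documents.

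**The concern.** The tube decides the matrix. A tube with EDTA does not let blood clot, and spinning it gives plasma. Serum comes only from clotted blood. The text and the handling note therefore ask for different materials from the same sample.

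This matters most for the functional read-out. Complement activation needs calcium and magnesium, and EDTA chelates both. That is general laboratory knowledge and not a statement in the protocol. If staff follow the text, deposition in blood could be lowered for a technical reason and read as weak antibody function. Objective 2 is to develop functional tools that might serve as a surrogate of protection, so a technical loss here would bear directly on that objective.

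The error would also be hard to repair. Cord blood cannot be collected again, section 9.4 expects no surplus blood, and the samples are batched before assay abroad, so a problem might surface only after many had been taken.

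**Working it through.** No power, alpha or event count is involved, so the check is a comparison of every place that names the tube or the matrix.

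| Place in the Protocol | Sample | Tube | Matrix |
|---|---|---|---|
| 5.2.2, running text | cord and 2-3 month infant | EDTA | plasma, by implication |
| 5.2.2, handling note | cord and 3 month infant | not named | serum |
| 5.2.2, Table 2, antibody row | blood | yellow | serum |
| 5.2.2, Table 2, complement row | blood | yellow | serum |
| 3.1, day 56-90 sample | infant | not named | serum |

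**Step 1: are these the same samples?** Yes. The running text and the handling note both cover cord blood and the later infant sample. The running text sends them to the same two assays that form the blood rows of Table 2.

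**Step 2: can the instructions be reconciled?** One might read the yellow tube as the storage tube and EDTA as the transport tube, because the yellow-tube entry is in the storage column. That would settle the tube but not the matrix: blood carried in EDTA and then spun gives plasma, whereas Table 2 and the handling note say serum.

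**Step 3: is this an effect of text extraction?** No. The EDTA sentence, the handling note and the antibody row are intact. Only the complement row is broken up, and its opening words are legible.

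**Step 4: what is exposed?**
- Endpoint 3 in blood: possible loss of deposition.
- Endpoint 3 in breast milk: not affected, since milk goes into sterile universal containers.
- Endpoint 2 in blood: complement blocking does not apply; the issue is consistency of serum with plasma.
- Endpoint 1 (carriage from swabs): not affected.

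**Step 5: how many samples?** The Protocol summary gives 100 mother-infant pairs and dropout of up to 20%. That makes up to 100 cord samples and, if all dropout falls before the last visit, 100 × (1 − 0.20) = 80 infant samples.

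**Step 6: what happens under each pattern of use?**
- Serum tubes throughout: no problem.
- EDTA throughout: no difference by tube, but possibly lower deposition in all blood samples.
- One tube for cord blood and the other for infant blood: observed change = true change + matrix effect. With tube fixed by visit, the two terms cannot be separated. Section 1.2 sets out to study antibody persistence and in-vitro function, so this pattern touches a stated aim. The regressions in section 7 that are run separately at each time point would each stay within one matrix.

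**The case against.** The strongest reply is that the intended matrix is clear. Serum appears in the handling note, in both blood rows of Table 2 and in section 3.1, and section 1.1 describes the complement assay as needing little serum. One contrary sentence looks like a drafting slip, and the SOPs presumably settle it. Much of this stands: the weight of the document is on serum, and an unsuitable design was probably not intended. But the EDTA sentence is an operative instruction on transport, and a reader of the protocol cannot tell which instruction the SOPs follow.

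The second reply concerns harm. If the assay adds complement from outside and uses pre-treated, highly diluted samples, carried-over EDTA may matter little. The assay is also meant to run on frozen breast milk, which is compatible with added complement, though the protocol does not say so. This stands as well, and it makes the harm possible and not certain.

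Three stronger readings are tempting, and the documents do not support them.

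- A reader might infer that endpoint 3 would be invalid. Only its blood part is exposed, and the protocol lacks the assay details needed to say how far.
- A reader might infer a bias by collector, because section 4.1 lets midwives or study staff take cord blood. Nothing suggests that they would use different tubes.
- A reader might conclude that EDTA samples should be dropped from the complement analysis. Without the assay details, that could discard usable samples that cannot be replaced, and all blood data for endpoint 3 if EDTA had been used throughout.

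**Conclusion.** The contradiction is certain. One sentence in section 5.2.2 requires a tube that yields plasma, and four other entries for the same blood require serum. The instructions cannot both be followed.

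The consequence is possible and of unknown size. It rests on two assumptions: that some staff follow the EDTA sentence, and that enough EDTA reaches the assay to bind calcium and magnesium. The loss in the blood part of endpoint 3 could then range from negligible to complete. The protocol gives no complement source, pre-treatment or dilution with which to narrow that range. A distortion of change over time in concentration or function needs the further assumption that tubes differ between the cord and infant visits.

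Because the samples are hard to replace and the correction is nearly free, it should be made before collection starts.

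**What to change.** 1. Before first collection, correct the EDTA sentence in section 5.2.2 so that one tube type and one matrix apply at both time points. Serum is the matrix in the handling note, Table 2 and section 3.1. Check that the SOPs say the same.
2. Record tube type for each blood sample on the worksheet already used for storage location.
3. If any EDTA sample is collected, flag it and report the complement analysis with and without it. Do not exclude it automatically.

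Stating the complement source and sample pre-treatment, or pointing to the SOP that gives them, would let a reader judge how much an EDTA sample matters.

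The cost is a one-line correction and one extra worksheet entry per blood sample. No further samples or visits are needed.

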6.1 Methods and timing for assessing, recording, and analysing safety parameters

Adverse events (AEs) or serious adverse events (SAEs) will be monitored during the study

6.1.1 Adverse event reporting procedure

If any adverse events occur which are directly related to the participation in the study, study staff will document these. Records will be in accordance with the MRC Gambia SAE reporting protocol

and include the following information: nature/description of the AE, start and stop date/time, severity of the AE and action taken. Staff will then monitor the events until their resolution.

6.2 Participant's premature termination

A study participant will be discontinued from participation in the study if:

- Intercurrent illness, or other medical condition or situation occurs such that continued participation in the study would not be in the best interest of the subject.
- Development of any exclusion criteria.

Subjects are free to withdraw from participating in the study at any time without giving a reason.

[figure not shown]
This withdrawal will not affect their standard medical care.

7 Statistical considerations

Sample Size:

Assume negatively correlated skewed distributions for maternal antibody and maternal (or infant) GBS load, with Figure 2 showing a typical simulated bi-variate distribution (note scale factor not modelled – correlation is unaffected). A sample size of 150 gives 90% power to detect a correlation of -0.45 as significantly different from zero at the 1% level (adjusted down to allow for serotype multiplicity).

Figure 2 Bi-variate distribution of antibody and bacterial load.

With the absence of further variability parameters it is not possible to conduct a classical sample size calculation. Although the study is powered on measuring correlation (i.e. linear trend), the analysis plan focuses on measuring the actual trend rather than relying on linear assumptions.

Analysis Plan

Initial analyses will be based on standard summary statistics comparing maternal and infant responses. Graphical methods with spline smoothers will be used to examine trends and if appropriate (linear trends), correlations will be used to summarize the relationships. Cross-tabulations will compare means (with 95% confidence intervals), medians (with inter quartile ranges), with histograms to compare distributions.

Formal analysis will be based on linear regression for each serotype and will test whether maternal antibodies predict colonization in newborns. Antibody responses will be suitably transformed to satisfy the normality and constant variance assumptions for the regression based analyses. As the relationships are likely to be non-linear fractional polynomials will be used to model non-linearity. In addition to analyses based on continuous data, responses will be categorized and contrasts used to make appropriate comparisons. Where possible regression will be adjusted for potential confounders including mothers with high levels of carriage who have not yet mounted an antibody response, infants without antibody and maternal and infant infections. With both maternal and infant longitudinal sampling, separate analyses will be repeated at each time point. Discrete analyses

based on carriage will be analyzed using a survival analysis approach. With multiple time points and multiple serotypes from the same subjects, false discovery rates will be used to control for false positives from multiple hypothesis tests.

8 Data handling and record keeping

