months a (4-5mL) blood sample will be taken from the infant by venipuncture as well as a nasopharyngeal and rectal swab and (4-5mL) sample of breast milk from the mother. Recruitment will be from the maternity ward at the Faji Kunda health centre, and restricted to healthy singleton infants, birth weight >2.5kg, without congenital abnormalities. Informed consent will be obtained from mothers. 100 pregnant women and their newborn infants will be recruited over 6-months (allowing for a dropout rate of up to 20%).

1 Background information and rationale

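### The only power statement is for a sample size of 150, but the protocol recruits 100 with up to 20% dropout, so the stated 90% does not describe this study

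*Protocol*

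**What the plan says.** The Sample Size paragraph of section 7 starts from a distributional assumption: "Assume negatively correlated skewed distributions for maternal antibody and maternal (or infant) GBS load". It then states that "A sample size of 150 gives 90% power to detect a correlation of -0.45 as significantly different from zero at the 1% level", the level having been lowered because several serotypes are tested. It adds that a classical sample size calculation is not possible without further variability parameters, and that the study is powered on correlation although the analysis will look at the actual trend.

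The protocol summary gives 100 as the number of participants. Its description of the design says that "100 pregnant women and their newborn infants will be recruited over 6-months (allowing for a dropout rate of up to 20" per cent).

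The figure of 150 appears only in section 7. It is not given anywhere as a recruitment target, and no power is given for 100 or for any smaller number.

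**The concern.** A power statement describes a study only at the sample size that the study will have. Here the justification uses half as many again as will be recruited (150/100 = 1.5), before any dropout.

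The second objective concerns the relation between maternal serotype-specific antibody and neonatal carriage, as a possible surrogate marker for vaccine trials. A weak or null association would be read against 90% power for a correlation of -0.45, and that power has not been shown for the sample enrolled. An ethics committee would also be reading a justification for a different number of women and infants.

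**Working it through.** **Inputs.** From section 7: n = 150, power 90%, correlation -0.45 against zero, 1% level. I read "significantly different from zero at the 1% level" as two-sided. The 1% equals 0.05/5 for the five serotypes in section 2.1. From the protocol summary: 100 recruited, up to 20% dropout, so 100 × (1 − 0.20) = 80 in the worst case. Assumption: one observation per mother-infant pair. Section 7 says only a sample size, but it also plans separate analyses at each time point, so visits are not pooled to reach 150.

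**Can dropout explain the gap?** No. Keeping 150 after a 20% loss needs 150/0.80 = 187.5, so 188 recruited. Starting from 100 gives 80 to 100.

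**Can the plan's own figure be reproduced?** That depends on the model, which the text does not specify.

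*Model A, bivariate normal (Fisher z).* Power = Φ(√(n−3) × atanh(0.45) − 2.576), with atanh(0.45) = 0.4847.
- n for 90%: ((2.576 + 1.282)/0.4847)² + 3 = 66.3, so 67
- n = 150: Φ(5.877 − 2.576) = 99.95%
- n = 100: Φ(4.774 − 2.576) = 98.6%
- n = 80: Φ(4.253 − 2.576) = 95.3%
- Smallest correlation detectable with 90% power, tanh(3.857/√(n−3)): 0.37 at 100, 0.41 at 80

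This does not return 90% at 150, but section 7 says that the data were assumed skewed and simulated, so it is not the protocol's model.

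*Model B, accept 90% at 150 and scale.* The non-centrality is 2.576 + 1.282 = 3.857 (unrounded inputs) at 150 and scales with √((n−3)/147).
- n = 100: 3.857 × √(97/147) = 3.133; Φ(3.133 − 2.576) = 71%
- n = 80: 3.857 × √(77/147) = 2.792; Φ(2.792 − 2.576) = 59%

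*Model C, skewed margins.* Gamma margins with shape 0.5 are joined by a Gaussian copula with -0.45 on the latent scale. A Pearson test at two-sided 1% is applied to 20,000 simulated data sets per n.
- n = 150: 90%
- n = 100: about 60%
- n = 80: about 40%

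With exponential margins on the same latent scale, power is about 90% at 100 and 79% at 80. If -0.45 is instead fixed on the raw scale, exponential and lognormal margins (log-scale SD 0.5 and 0.75) give at least 99% at 80, 100 and 150.

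| Assumption | n = 150 | n = 100 | n = 80 |
|---|---|---|---|
| A: bivariate normal | 99.95% | 98.6% | 95.3% |
| B: scaled from 90% at 150 | 90% | 71% | 59% |
| C: gamma(0.5), latent -0.45 | 90% | 60% | 40% |

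The answer turns on the shape of the margins and on the scale on which -0.45 is set. The text gives neither. The accompanying figure is not in the copy at hand.

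**The case against.** **The protocol did not use a normal-theory formula.** This stands. A reader might infer from Model A that 150 for 90% is an arithmetic error, since 67 would be enough. The document does not support that: it describes a skewed simulation, and Model C shows that the stated combination is attainable under skewed margins. It does not show that the sponsor used that model.

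**A shortfall is not proven.** This also stands. A reader might infer that the study is underpowered, or that its power at 80 lies between 59% and 95%. Neither follows. Models A to C are assumptions, and other plausible skewed models fall outside both ends of that interval. Normality is itself doubtful: section 7 transforms only antibody responses, and with the maternal carriage of 22 to 24% cited in section 1.1, most load values could be zero.

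**Eighty is a worst case, mainly for later visits.** This largely stands. Section 3.1 takes cord blood and the maternal swab at delivery and the first infant swabs within 24 hours, and section 4.1 places final enrolment after birth. About 100 is therefore the relevant number for the birth analysis. Section 3.1 also mentions recruitment at 37 weeks, so some loss before delivery is possible.

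**The first objective is descriptive, and section 7 says that the analysis will not rely on linearity.** This is true, but section 7 still says that the study is powered on correlation.

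None of these points links 150 to 100.

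**Conclusion.** The inconsistency is real and rests on the text alone: the only power statement is for 150, recruitment is 100 with up to 20% dropout, and nothing connects them. The stated 90% power does not describe this study.

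How far the true figure is from 90%, and in which direction, cannot be derived from the protocol text. The illustrations run from 98.6% down to 60% at 100, and from 95% down to 40% at 80; they are not limits. They assume a two-sided 1% test, one observation per mother-infant pair and, for 80, the full 20% loss. Confidence is high for the mismatch only. The document does not say which of 150 and 100 is the intended number.

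**What to change.** Reconcile the 150 in section 7 with the 100 in the protocol summary, and state the expected evaluable number at each time point.

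If enrolment stays at 100, replace the power sentence. Re-run the same simulation at about 100 for the birth analysis and down to 80 for later visits. Report either the power for -0.45 at the 1% level or the smallest correlation detectable with 90% power. State the marginal distributions, the scale on which the correlation is defined and the sidedness of the test, so that the figure can be checked.

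This point does not itself call for higher enrolment. The cost is one re-run of an existing simulation and one reworded paragraph; the price may be a stated power less favourable than 90%.
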